14.3.1 Statement for Secondary Endpoints

Secondary Endpoints include:

Maximum Toxicity Grade:

The maximum grade of each type of toxicity will be recorded for each patient. For each toxicity reported by dose level, the percentage of patients developing any degree of that toxicity as well as the percentage of patients developing a severe degree (Grade 3 or higher) will be determined.

Number/Duration of Response:

For each dose level, the number of response and the duration of response will be tabulated. The duration of response is the time from initiation of first response to first documentation of disease

progression or death. Patients who have not progressed will be censored at the date of their last disease evaluation.

Progression-free Survival (PFS)/ Overall Survival (OS)

Secondary endpoints for the expansion cohort include progression-free survival (PFS) and overall survival (OS) time.

Survival time is defined as the time from study entry to death due to any cause.

Progression-free survival time is the time from study entry to the documentation of disease progression or death due to any cause.

If a patient dies without a recurrence documented, the patient will be censored at the date of last disease evaluation. The distribution of response times, progression-free survival times and survival times will be estimated using the Kaplan-Meier method.

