Secondary Objectives	
To determine the following:
 
 1. Progression-free survival (PFS): Time from registration to disease progression or death due to any cause. 2. Overall survival (OS): Time from registration to death due to any cause. 3. Overall Response Rate: Time from start of treatment to objective response 4. Duration of response: Time from documented response to disease progression among those patients whose disease meets the IMWG criteria for disease response
Correlative Science Objectives	To perform select immunologic studies with this combination therapy.
Study Design	
Part 1: Dose Escalation
 
Patients in the dose escalation phase will receive oral treatment with:
 
Ibrutinib: Days 1-28 of every 28-day cycle Lenalidomide: Days 1-21 of every 28-day cycle Dexamethasone: 40 mg for patients <75 at the time of registration 20 mg for patients ≥ 75 at registration on Days 1, 8, 15 and 22 of every Cycle. One cycle is 28 days.
 
Starting doses of ibrutinib and lenalidomide will be assigned at the time of registration. A minimum of 2 or a maximum of 6 patients will be accrued to a given dose level. Doses will not be escalated in any individual patient. If none of the first 3 patients treated at a given dose level develops a DLT during the first cycle of treatment, enrollment to the dose level will be closed and enrollment will reopen at next higher dose level. If there are no other higher dose levels to be tested, three additional patients will be enrolled at the current dose level to confirm MTD. If one of the first 3 patients treated at a given dose level develops a DLT during the first cycle of treatment, three additional patients will be enrolled onto the current dose level. If, at any time in the enrollment of these 3 additional patients, a patient develops a DLT, enrollment will be closed to this dose level. Enrollment will be reopened to the next lower dose level if fewer than 6 patients have been treated at that dose level. If none of these 3 additional patients develops a DLT during the first cycle of treatment, enrollment to this dose level will be closed and enrollment will reopen at next higher dose level. If

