2.4. Endpoints

2.4.1 Primary and Secondary

Primary:

1. Maximum tolerated dose (MTD): The maximum tolerated dose (MTD) is defined as the highest dose level among those under consideration where at most 1 of 6 patients develops a dose limiting toxicity and 2 or more of the 3-6 patients treated at the next higher dose level develop a dose limiting toxicity.
2. Safety profile: The maximum grade of each type of toxicity will be recorded for each patient. For each toxicity reported by dose level, the percentage of patients developing any degree of that toxicity as well as the percentage of patients developing a severe degree (Grade 3 or higher) due to treatment will be determined.

Secondary:

1. Progression free survival (PFS) defined as the time from study entry to the documentation of disease progression using IMWG criteria or death due to any cause.
2. Overall survival (OS) is defined as time from registration to death due to any cause.
3. Overall Response rate(ORR)
4. Duration of response, defined as the time from documented response to disease progression among those patients whose disease meets the IMWG criteria for disease response.
5. Safety Profile: CTCAE v5.0 will be used to grade and assign attribution to each adverse event reported.

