14.3.2 Statement for Primary Endpoint

The primary endpoint of the dose escalation portion of this phase I study is the MTD. The maximum tolerated dose is defined as the highest dose level among those tested where at most one out of 6 patients develops a DLT prior to the start of their second cycle of treatment and the next highest dose level is such that 2 or more patients among the maximum of 6 patients treated at that dose level developed a DLT prior to the start of their second cycle of treatment.

The primary endpoint of the expansion portion of this phase I study is the objective response rate. The objective response rate is the percent of patients who meet the International Myeloma Working Group Response Criteria for sCR, CR, VGPR, or PR on two consecutive evaluations at least 4 weeks apart among the patients who began study treatment. A 90% binomial confidence interval will be constructed for the overall objective response rate.

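### Duration of response ends at progression in the synopsis and 2.4.1 but at progression or death in 14.3.1, whose censoring sentence then censors the same deaths

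*Combined protocol and SAP*

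**What the plan says.** Three places define duration of response.

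- Synopsis, Secondary Objectives, item 4: "Duration of response: Time from documented response to disease progression among those patients whose disease meets the IMWG criteria for disease response".
- Section 2.4.1, secondary endpoint 4: "Duration of response, defined as the time from documented response to disease progression among those patients whose disease meets the IMWG criteria" for response.
- Section 14.3.1, Statement for Secondary Endpoints: "The duration of response is the time from initiation of first response to first documentation of disease" and, continuing, "progression or death. Patients who have not progressed will be censored at the date of their last disease evaluation".

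The PFS/OS paragraph of 14.3.1 adds: "If a patient dies without a recurrence documented, the patient will be censored at the date of last disease evaluation". The next sentence reads: "The distribution of response times, progression-free survival times and survival times will be estimated using the Kaplan-Meier method".

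On confirmation of response, section 14.3.2 requires the criteria to be met "on two consecutive evaluations at least 4 weeks apart among the patients who began study treatment", while section 13.4 sets the minimum gap at 6 weeks. Nothing in the documents says which definition of duration of response governs.

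**The concern.** Take a responder who dies, say of infection or bleeding, with no progression on record. The synopsis and 2.4.1 give no event for this patient. The definition in 14.3.1 gives an event at death. The sentence directly after it gives a censored time at the last disease evaluation. Two analysts could each follow the protocol faithfully and code this patient differently.

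The omission of death in the synopsis and 2.4.1 cannot be dismissed as shorthand. Both lists name death from any cause for PFS and leave it out for duration of response, so a reader could take it as intended.

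Such deaths are plausible here. Section 1.4.2 reports fatal hemorrhage and infections associated with death on ibrutinib, and treatment-related death is listed among the dose-limiting toxicities in Table 9. If the choice of rule is left until analysis, it will be made after the deaths are known. Censoring them would also make the duration look longer the more responders die in response, which is unhelpful in a trial where safety is a primary objective.

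**Working it through.** The plan gives no expected duration of response, so there is no figure to reproduce. The check compares the rules and then illustrates the size of the difference.

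**1. The rules side by side, for a responder who dies without documented progression**

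| Source | Start | Status of the death |
|---|---|---|
| Synopsis, item 4 | documented response | not named; progression is the only end |
| 2.4.1, endpoint 4 | documented response | not named; progression is the only end |
| 14.3.1, definition | initiation of first response | event |
| 14.3.1, next sentence | – | censored at last disease evaluation |
| 14.3.1, PFS/OS paragraph | – | censored at last disease evaluation, if the sentence covers response durations |

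The last row is a possible reading because the sentence that follows it speaks of response times together with PFS and survival times.

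**2. Size under constant hazards (illustration)**

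Let λp be the hazard of progression and λd the hazard of death without progression, and let f = λd/(λp + λd) be the share of events that are such deaths.

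- Median, progression or death: ln 2/(λp + λd).
- Median, progression only with deaths censored: ln 2/λp.
- Ratio of the second to the first: (λp + λd)/λp = 1/(1 − f).

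With f = 0.10 (assumed): 1/0.90 = 1.11. With f = 0.20 (assumed): 1/0.80 = 1.25. An assumed median of 10.0 months would become 11.1 to 12.5 months.

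**3. Size with few responders (illustration on assumed data)**

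Six responders have times from first response of 3, 5, 8, 10, 14 and 18 months. The last is censored and the others are events. The last disease evaluation is taken as 1 month before any death. The median is the first time at which the Kaplan-Meier estimate is 0.50 or lower.

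- Progression or death: 5/6, 4/6, 3/6 at 3, 5 and 8 months, so the median is 8 months (5 events), whichever of these events are deaths.
- No deaths without progression: progression only also gives 8 months.
- One such death (the patient at 5 months, censored at 4): 5/6 at 3 months; × 3/4 = 0.625 at 8; × 2/3 = 0.417 at 10. The median is 10 months (4 events).
- Two such deaths (also the patient at 10 months, censored at 9): 0.625 at 8 months; × 1/2 = 0.312 at 14. The median is 14 months (3 events).

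The 8-month estimate sits exactly at 0.50. Software that reports the midpoint of the flat stretch would give (8 + 10)/2 = 9, which narrows the gaps but does not close them.

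**4. Start date**

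If documented response means the first assessment showing response, the two start dates coincide and the shift is 0. If it means the confirming assessment, each duration is shorter by at least 28/30.4375 = 0.9 month (14.3.2) or 42/30.4375 = 1.4 months (13.4).

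**The case against.** The case for leaving this alone has several parts.

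- Section 14.3 is headed as the place for endpoint definitions and the analysis plan, so an analyst would look there first. That is fair, but 14.3.1 contradicts itself on the patient in question, so going there does not settle the matter.
- The endpoint is secondary, descriptive and uncontrolled. It drives no test, sample size, stopping rule or dose decision. This stands and limits the weight of the point.
- The results differ only if a responder dies without documented progression. This also stands; with no such death the readings agree.
- Section 14.3.1 says duration of response will be tabulated by dose level. The response times to be estimated by Kaplan-Meier could mean time to response, since the synopsis describes its response item as a time from start of treatment. This stands as a caution: Kaplan-Meier estimation of duration is one reading. A tabulation still has to mark each duration as complete or censored, so the conflict remains.
- Progression-only duration is a legitimate quantity in its own right. True; the censored version overstates only if the target is time alive and in response.

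A reader might also infer that the differing start wording moves every duration by at least 4 weeks. The documents do not support that, because they never say that documented response means the confirming assessment. Nor do the synopsis and 2.4.1 state that deaths are censored; they give no censoring rule, and that treatment is only the natural consequence of a progression-only end.

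**Conclusion.** The inconsistency is real and concerns the handling of death. Two places end duration of response at progression. The third ends it at progression or death and then, read literally, censors deaths without progression. No text resolves this.

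The size depends on events not yet known. The factor of 1.11 to 1.25 rests on constant hazards and an assumed 10 to 20% share of deaths without progression. It is not a forecast for this trial. With 19 to 25 patients over up to three dose levels and tabulation by level, responders per level will be few, and a single death may move the result or leave it unchanged.

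The start date is an ambiguity worth closing, worth 0 or about 0.9 to 1.4 months depending on the meaning given to one word. The MTD, the safety summaries, the response rate and the sample size are not touched. The point merits correction before analysis because the text gives conflicting instructions and the remedy is cheap.

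**What to change.** 1. Use one definition in the synopsis, 2.4.1 and 14.3.1: from the first assessment at PR or better that is later confirmed, to first documented progression or death from any cause, whichever comes first.
2. Replace the 14.3.1 censoring sentence with one that censors only patients who are alive and progression-free, at their last disease evaluation.
3. Delete the PFS/OS sentence that censors deaths without documented recurrence, or state that it does not apply to duration of response. Without this step, 14.3.1 could still be read as censoring the deaths that step 1 counts. Deleting it also changes how PFS is handled, so that should be a deliberate choice.
4. Reconcile the 4-week and 6-week confirmation intervals in 14.3.2 and 13.4. With the start fixed at the first qualifying assessment, the interval decides who counts as a responder but no longer moves the start date.

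The cost is wording only, using data the trial already collects. The reported duration may be shorter than under the progression-only reading: by the share f in the constant-hazard illustration, so 10 to 20% under the assumed values, and not at all if no responder dies without progression.

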2.2. Secondary Objectives

The secondary objectives of this study are:

1. To determine progression-free survival (PFS)
2. To determine overall survival (OS)
3. To determine duration of response
4. To determine overall response rate (ORR)

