2.4.2 Correlative

1. Immunologic studies: bone marrow aspirate and peripheral blood samples will be collected from patients for immunome studies. See Protocol Section 13 for more information.

3. Patient Selection / Population

19-25 patients (9-18 dose escalation; 4-10 dose expansion) with symptomatic multiple myeloma (as defined by IMWG criteria) will be enrolled across multiple investigational sites in the United States. Screening labs must be performed within 7 days prior to registration. Complete body CT scan if clinically indicated at screening must be performed within 14 days prior to registration.

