8.3. Criteria for Discontinuation of Protocol treatment

Patients are continued on treatment until any of the criteria for discontinuation of protocol therapy is met, which includes:

- Tumor progression
- Request by the patient to withdraw
- Unacceptable adverse events
- Treatment delay of >4weeks
- Intercurrent illness which would, in the judgment of the investigator, affect assessments of clinical status to a significant degree or require discontinuation of drug

Administration of non-protocol anti-tumor drug during the trial. Patients who discontinue treatment for any of the above reasons will go to survival follow-up where late toxicities and clinical outcome information will be collected every 6 months for a maximum of 2 years post registration. Once a patient has entered the survival follow-up phase of the trial, his/her therapy is at the discretion of the treating physician.

9. Study Assessments and Procedures

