14.1. Overview of the Study Design

This is a single-arm, open label, phase Ib study of Ibrutinib in combination with lenalidomide and dexamethasone in adult (age 18 years and older) patients with relapsed/refractory MM. A 3+3 phase I clinical trial design as described in Section 6.0 was chosen to determine the MTD of Ibrutinib in combination with lenalidomide given on days 1-21 of a 28-day cycle and dexamethasone given orally weekly. An expansion cohort of 10 patients will be treated at the MTD to gather additional safety and anti-tumor activity data.

As of April 15, 2021, 2 patients have been enrolled onto dose level 2.

- If none of the first 3 patients treated at dose level 2 develops a DLT, then the next cohort of 3 patients will be enrolled onto dose level 3 and biospecimen collection will begin for all subsequent patients enrolled.
- If one of the 3 patients treated at dose level 2 develops a DLT, then the next cohort of 3 patients will be enrolled at dose level 2 and correlative biospecimens will be collected from these patients.
 - o If 2 or more of the 6 patients treated at dose level 2 develops a DLT then an additional 10 patients will be enrolled onto dose level 1 so that a total of 10 patients will have provided biospecimens at the MTD. (Note: Total sample size will be 6 [from dose level 1] + 6 [from dose level 2] + 10 [for dose expansion] = 22. Biospecimens will be available for 10 patients treated at the MTD.)
- If 2 or more of 3 patients treated at dose level 2 has an DLT, an additional 10 patients will be enrolled onto dose level 1 to further assess safety and collect specimens for correlative aims. (Note: Total sample size will be 6 [from dose level 1] + 3 [from dose level 2] + 10 [for dose expansion] = 19. Biospecimens will be available for 10 patients treated at the MTD.)
- If at most 1 of 6 patients treated at dose level 2 develops a DLT and 2 or more of the 3-6 patients treated at dose level 3 develops a DLT, then an additional 7 patients will be enrolled onto dose level 2 so that a total of 10 patients will have provided biospecimens at the MTD. (Note: Total sample size will be 6 [from dose level 1] + 6 [from dose level 2] + 6 [maximum number anticipated on dose level 3] + 7 [for dose expansion] = 25. Biospecimens will be available for 10 patients treated at the MTD.)

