14.3. Definitions of Endpoints and Analysis Plan

14.3.1 Patient Evaluability

All patients meeting the eligibility criteria who have signed a consent form and have begun treatment will be included in the analysis of the safety and clinical outcome data.

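### The analysis plan attaches PFS and OS to the expansion cohort alone, against its own evaluability rule and the study-level objectives; the analysis population must be stated

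*Combined protocol and SAP*

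**What the plan says.** Under PFS/OS, the Statement for Secondary Endpoints reads "Secondary endpoints for the expansion cohort include progression-free survival (PFS) and overall survival (OS) time". The Kaplan-Meier method is named a few lines later without a population. Nothing else in Section 14 assigns PFS or OS to escalation patients. The same statement breaks toxicity and response down by dose level, so escalation patients are covered there.

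Patient Evaluability (also numbered 14.3.1) is general: patients who are eligible, have consented and "have begun treatment will be included in the analysis of the safety and clinical outcome data". It does not distinguish the two parts of the study.

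The synopsis and Sections 2.2 and 2.4.1 list PFS and OS for the study as a whole. For example, "Overall survival (OS) is defined as time from registration to death due to any cause". None of these places names a cohort.

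On conduct, the synopsis gives expansion patients the MTD on the escalation schedule with the same dexamethasone dose. Section 8.3 sends all patients who stop treatment to follow-up, where "clinical outcome information will be collected every 6 months for a maximum of 2 years post registration".

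The expansion size depends on the branch in Section 14.1. Two examples are "Total sample size will be 6 [from dose level 1] + 6 [from dose level 2] + 10 [for dose expansion] = 22" and, for another branch, "6 [maximum number anticipated on dose level 3] + 7 [for dose expansion] = 25". Sections 1.2 and 14.1 also state a flat expansion of 10.

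**The concern.** Two statisticians could follow this plan and report different populations. One would apply the evaluability rule and include everyone treated. The other would apply the PFS/OS statement and use the expansion cohort. That choice should not be made after the data are seen.

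The narrower choice also costs precision where the study has least to spare. Section 14.1 sizes the expansion to bring the number of patients with biospecimens at the MTD to 10, not to estimate survival. When level 3 is the MTD, it reaches 10 by adding 4 expansion patients to 6 escalation patients. For biospecimens the plan thus already combines the two groups, yet PFS and OS would rest on the 4 alone. The documents give no reason for treating the endpoints differently.

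**Working it through.** **Step 1. Reproduce the plan's totals.** Inputs are the cohort sizes in the Section 14.1 branches. Total = escalation patients + expansion patients. Share left out = escalation patients at the MTD / all patients at the MTD.

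| Branch (DLT outcome) | Escalation, levels 1+2+3 | Expansion | Total | At MTD, pooled | Left out if expansion only |
|---|---|---|---|---|---|
| Level 2: 2 or more of 6 | 6+6 | 10 at level 1 | 22 | 6+10 = 16 | 6/16 = 38% |
| Level 2: 2 or more of 3 | 6+3 | 10 at level 1 | 19 | 6+10 = 16 | 6/16 = 38% |
| Level 2: at most 1 of 6; level 3: 2 or more | 6+6+6 | 7 at level 2 | 25 | 6+7 = 13 | 6/13 = 46% |
| Level 2: at most 1 of 6; level 3: at most 1 of 6 | 6+6+6 | 4 at level 3 | 22 | 6+4 = 10 | 6/10 = 60% |
| 3 patients at level 2; level 3: at most 1 of 6 | 6+3+6 | 4 at level 3 | 19 | 6+4 = 10 | 6/10 = 60% |
| 3 patients at level 2; level 3: 2 or more | 6+3+6 | 7 at level 2 | 22 | 3+7 = 10 | 3/10 = 30% |

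All six totals agree with Section 14.1.

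**Step 2. Whole study.** Patients outside the expansion number 12/22, 9/19, 18/25, 18/22, 15/19 and 15/22, in table order. The share runs from 9/19 = 47% to 18/22 = 82%.

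**Step 3. Flat expansion of 10.** If the flat figure applied instead, the omission at the MTD would be 6/(6+10) = 38%, or 3/(3+10) = 23% where only 3 patients had been treated at level 2. The omission shrinks on most branches but does not go away.

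**Step 4. Precision of a landmark estimate.** The documents give no PFS or OS rate and no precision target, so the landmark rate S is assumed. With no censoring before the landmark, the Kaplan-Meier estimate is a proportion and SE = sqrt(S(1-S)/n).

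- S = 0.5: n=4, sqrt(0.25/4) = 0.250; n=7, 0.189; n=10, 0.158; n=13, 0.139; n=16, 0.125.
- S = 0.3 or 0.7: n=4, sqrt(0.21/4) = 0.229; n=7, 0.173; n=10, 0.145; n=13, 0.127; n=16, 0.115.

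The ratio of pooled to expansion-only SE is sqrt(expansion n / pooled n), whatever S is: sqrt(10/16) = 0.79 at level 1; sqrt(7/13) = 0.73 or sqrt(7/10) = 0.84 at level 2; sqrt(4/10) = 0.63 at level 3.

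**Step 5. Exact 90% intervals at an observed 50%.** The Clopper-Pearson limits are the 5% quantile of Beta(x, n-x+1) and the 95% quantile of Beta(x+1, n-x).

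- 2 of 4: 0.098 to 0.902.
- 5 of 10: 0.222 to 0.778.
- 8 of 16: 0.279 to 0.721.

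**The case against.** The statement says that the endpoints for the expansion cohort include PFS and OS; it does not say only. The Kaplan-Meier sentence names no cohort and also covers response times, and response is reported by dose level. A statistician could therefore apply the evaluability rule and include everyone. This stands in part: a reader might infer that the plan expressly excludes escalation patients, and it does not. But if the statement is not a restriction, the PFS/OS population is not clearly fixed, and the same edit is needed.

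An expansion-only analysis is also coherent. Section 14.3.2 gives each part its own primary endpoint, and Section 14.1 says the expansion is there to add safety and activity data. That explains the wording, but it does not reconcile it with the evaluability rule or the study-level objectives.

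The best statistical argument is selection. A level becomes the MTD partly because its escalation patients had few DLTs, so the pooled set is not fully independent of the choice of dose. This is a fair reason to show the expansion cohort separately as well. It is a small downside for PFS and OS, not a reason to leave those patients out.

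Some patients start below the nominal dose for renal or hepatic function. Those provisions are not specific to either part, and grouping by assigned dose level deals with them.

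**Conclusion.** The inconsistency is real and worth correcting, though the endpoints are secondary and descriptive. The PFS/OS statement points to the expansion cohort, the evaluability rule points to all eligible treated patients, and the objectives name no cohort. Taken as written, the statement leaves 10, 7 or 4 patients and omits 30% to 60% of those assigned to the MTD by the Section 14.1 branches. These counts come from the documents. The intervals and standard errors rest on an assumed landmark rate and no earlier censoring.

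Three stronger readings are not supported:

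- **Section 2 prescribes an all-treated analysis.** It names no population. Only the evaluability rule does, and that rule also requires eligibility.
- **30% to 60% of the time-to-event information is lost.** The figure is a share of patients; information depends on events and follow-up.
- **A curve on 4 patients fails the objective while the pooled one meets it.** The plan sets no precision target, and 10 patients still give 22-78% at an assumed 50%. Pooling makes the estimate better, not precise.

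**What to change.** Replace the PFS/OS sentence in the Statement for Secondary Endpoints with wording such as: *PFS and OS will be estimated by the Kaplan-Meier method in all eligible patients who began treatment, as defined under Patient Evaluability, and presented by assigned dose level. The main estimate pools escalation and expansion patients assigned to the MTD. Results for the expansion cohort alone will be given as a sensitivity analysis.*

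Name the same population in Sections 2.2 and 2.4.1 and in the synopsis. Reconcile the flat expansion of 10 in Sections 1.2 and 14.1 with the branch-specific 10, 7 or 4, so that the reported denominators are clear. Note in the report that escalation patients at the MTD contributed to selecting that dose.

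The cost is a few lines of text. No extra patients, visits or data are needed, because follow-up under Section 8.3 already applies to both parts. The change should be made before the outcome data are analysed.

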- i. Immunoglobulins, serum free light chains (kappa and Lambda), serum monoclonal protein, beta 2 microglobulin ≤ 14 days prior to registration and day 1 of each cycle. 24-hour Urine Protein and immunofixation ≤ 14 days prior to registration, and every 3 months.

10. Adverse Events

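### The PFS analysis text contradicts itself: death is an event in the definition, but a patient who dies without documented recurrence is then censored, which generally overstates PFS

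*Combined protocol and SAP*

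**What the plan says.** Three places define PFS, and all count death as an event:

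- Synopsis, Secondary Objectives: "Time from registration to disease progression or death due to any cause".
- Section 2.4.1: time to "documentation of disease progression using IMWG criteria or death due to any cause".
- Section 14.3.1, Statement for Secondary Endpoints: "Progression-free survival time is the time from study entry to the documentation of disease progression or death due to any cause".

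The sentence after that last definition reads: "If a patient dies without a recurrence documented, the patient will be censored at the date of last disease evaluation". The section then names Kaplan-Meier as the estimator for response times, PFS and survival. (The number 14.3.1 is used twice; the second use is meant here.)

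On the population, the same section says "Secondary endpoints for the expansion cohort include progression-free survival (PFS) and overall survival (OS) time". Section 14.3.1, Patient Evaluability, sets no such limit: eligible, consented patients who "have begun treatment will be included in the analysis of the safety and clinical outcome data".

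**The concern.** A death without documented progression is an event under the definition and a censored observation under the next sentence. If the sentence is followed, only documented progression remains an event. The result is a time-to-progression curve under the name PFS, with death treated as non-informative censoring and dated back to the last evaluation. Two analysts could follow the same section and report different PFS.

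Such deaths are foreseeable. Table 9 lists treatment-related death as a DLT, and Sections 1.4.2.1 and 1.4.2.3 describe fatal bleeding and infections associated with death under ibrutinib. In a trial whose primary objectives include safety, the more favourable figure would come from treating toxicity deaths as non-events. If the choice between the two sentences is left until the deaths are known, it becomes data-dependent.

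**Working it through.** **Can another reading remove the conflict?**

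- Overall survival: no, because death is its event.
- Duration of response: no. In Section 14.3.1 it ends at progression or death and has its own censoring sentence, for patients who have not progressed.
- A time-to-progression endpoint, a deaths-censored sensitivity analysis or a rule of precedence: none is given.
- A drafting slip for patients alive without progression: possible, since the PFS text has no other censoring rule for them. As written, though, the sentence addresses patients who die.

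The plan states no PFS rate, median or event count, so there is no planned figure to reproduce. The size can be shown in two ways.

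**1. Exact examples, without a hazard assumption**

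Inputs: Section 14.1 adds 4, 7 or 10 expansion patients and plans totals of 19 to 25. Assume that every patient is followed to an event, with no other censoring. After the k-th of n events the defined PFS is (n − k)/n. A death in position j that is censored loses its factor (n − j)/(n − j + 1), so

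estimate = (n − k)/n × product over such deaths of (n − j + 1)/(n − j).

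The lowest value has the deaths first in the ordering and the highest has them last. Dating a death back only moves it to an earlier position, which the range already covers.

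For n = 10, k = 5:

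- one death: 0.5 × 10/9 = 0.556 to 0.5 × 6/5 = 0.600;
- two deaths: 0.5 × 10/8 = 0.625 to 0.5 × 7/5 = 0.700.

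| n | After event | PFS as defined | One such death | Two such deaths |
|---|---|---|---|---|
| 4 | 2nd | 50% | 67–75% | – |
| 7 | 4th | 43% | 50–57% | 60–71% |
| 10 | 5th | 50% | 56–60% | 63–70% |
| 19 | 10th | 47% | 50–53% | 53–58% |
| 25 | 13th | 48% | 50–52% | 52–56% |

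The word generally is needed, because backdating can lower the curve briefly before the death. With n = 10, if the third event is a death censored before the first event, the estimate after the second event is 8/9 × 7/8 = 0.778, against 0.80.

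**2. Illustration on assumed inputs**

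Assumed, not in the documents: constant hazards, a true median of 5.0 months, and a share f of 10, 20 or 30% of first events being such deaths. Progressions keep their own times; deaths are censored at the last evaluation. The evaluation interval g comes from Table 15, footnote i: serum markers are due at "days prior to registration and day 1 of each cycle" (28 days), and 24-hour urine every 3 months. The latter matters for patients eligible on urine protein alone (Section 3.1).

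With S(t) = exp(−ln 2 × t/5), the Kaplan-Meier factor for t between mg and (m + 1)g is

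[(1 − f)S(t) + f S((m + 1)g)] / [(1 − f)S(mg) + f S((m + 1)g)],

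multiplied over intervals.

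| g | Median at f = 10/20/30% (true 5.0 months) | 6-month PFS (true 43.5%) |
|---|---|---|
| 28 days | 5.52 / 6.17 / 7.01 | 47 / 51 / 55% |
| 3 months | 5.45 / 6.02 / 6.72 | 47 / 50 / 54% |

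As a check, with continuous evaluation the median is multiplied by 1/(1 − f): 5/0.9 = 5.56, 5/0.8 = 6.25 and 5/0.7 = 7.14 months. The tabulated values lie slightly below these, as backdating implies.

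**The case against.** **It is probably a slip.** Three definitions count death, and the duration-of-response sentence follows the usual pattern of censoring patients who have not progressed. Most analysts would follow the definition. That is likely, but a literal reader could follow the sentence, and it is the only PFS censoring rule given.

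**The shift is small against the sampling error.** PFS carries no test, threshold or decision. With 5 of 10 patients event-free, the exact 95% interval is 19–81%, and a one-death shift of 6–10 points lies well inside it. This limits the weight of the point. It does not excuse an avoidable bias that runs generally one way.

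**The illustration times progression unrealistically.** PFS runs to documentation of progression, which happens at evaluations. If progression is recorded at the next evaluation, on the same assumed hazards, the defined median is 5.52 months with 28-day evaluations and the censored one reads 6.44/6.44/7.36. With 3-month evaluations the defined median is 6.0 and the censored one reads 6.0/9.0/9.0. This is correct. The two-decimal medians in the illustration depend on the timing convention, and the 3-month case would apply to only some patients. No median falls, though one setting shows no change, and the exact examples do not depend on this.

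**Such deaths may be few, and the small cohorts exaggerate.** The Synopsis provides for chart review for progression in follow-up, which should reduce deaths without documented progression. The n = 4 and n = 7 rows count only the added patients, whereas Section 14.1 also speaks of an expansion cohort of 10. Both points are fair; the rows for 10, 19 and 25 show the smaller effects.

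**Conclusion.** The concern holds. The censoring sentence is wrong as written: it conflicts with all three PFS definitions and nothing in the documents reconciles them. If it is followed and such deaths occur, PFS is generally overstated. At the points tabulated, one such death adds about 6–10 percentage points with 10 patients and about 2–5 points with 19 to 25. The effect is larger if the cohort is only 4 or 7. These figures assume complete follow-up to an event; the medians and 6-month values rest on assumed hazards and shares. If no patient dies without documented progression, the bias is zero.

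The consequence is confined to a descriptive secondary endpoint. Such deaths still count in overall survival. The MTD and sample size do not depend on the sentence, and the response rate is taken "among the patients who began study treatment". It should be fixed before analysis, but it does not threaten the primary results.

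**What to change.** Replace the sentence in Section 14.3.1 with: *Patients who die without documented progression have a PFS event at the date of death; patients alive without progression are censored at the last disease evaluation.* If a deaths-censored curve is also wanted, label it time to progression.

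A separate, minor consistency edit: the Synopsis and Section 2.4.1 define duration of response without death, while Section 14.3.1 includes it. Align them on progression or death, censoring only patients alive without progression.

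The PFS change costs one sentence and needs no new data. Estimates stay the same if there are no such deaths. Otherwise the reported PFS will generally be lower than under the censoring sentence, by amounts of the order tabulated.
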